### 5.2.2 Screen Failures/Dropouts

A subject who discontinues study participation prematurely for any reason is defined as a "dropout" if the subject has already been randomized; assigned to treatment/run-in/wash-out; administered at least one dose of study drug.

A subject who, for any reason (e.g. failure to satisfy the selection criteria), terminates the study before the time point used for the definition of "dropout" (see above) is regarded a "screening failure".

### **5.2.3 Replacement**

No withdrawn subjects will be replaced.

## **6. Treatment[s]**

We will randomize 96 eligible patients in the Biostatistics Clinical Trial Conduct website to receive either Icosapent ethyl (Vascepa) 2 gm orally daily plus physical activity, or placebo plus physical activity, or placebo plus control PA(1:1:1) for 8 weeks (see treatment schema below).

[figure not shown]

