### **4. Study Design**

#### **4.1 Study population**

Patients with advanced cancer will be recruited from UTMDACC. At UTMDACC, patients will be recruited from medical oncologists working in outpatient clinics, and in our own outpatient supportive care center. Patients will be screened for eligibility criteria. Patients who are eligible and who provide written informed consent to participate in this research study will be admitted to the double-blind phase of the study described below. Consent forms and assessments will be available and administered by the study-assigned research nurse. Feasibility: Is based on the prior successful accrual in similar symptom control trials by our group in these sites and great interest in Complementary and Alternative Medicine (CAM) in this population (48%).

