### **6.1 Treatments to be administered**

In this study, patients will be randomized to either combination of Icosapent ethyl 2 gm orally daily plus physical activity; or placebo plus PA or placebo plus control PA for 8 weeks (See Fig. 3 below for the treatment schema). The placebo will be identical to the drug, but will contain methylcellulose as the inert ingredient. Assessment will be performed at baseline to Day  $57\pm5$  as per Table 4.

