#### **Icosapent ethyl (Vascepa)**

In the proposed study we plan to use fish oil preparation, Icosapent *ethyl* [an ethyl ester of EPA] 0.5 gram capsules [Amarin Pharma Inc, Bedminster, NJ, 2012]. The placebo will be identical to the drug, but will contain methylcellulose as the inert ingredient. Assessment will be performed at baseline to Day  $57\pm5$ . The objective of 8 weeks of treatment is to evaluate the efficacy of the combined intervention for cancer related fatigue.

The rationale for placebo and control arm for PA is to control for placebo effect, attention to participant's expectation and the subjective elements of diagnosis or assessment. See Table 4 for the study assessments. All patients at the primary end point (8 weeks) will have an option to receive Icosapent ethyl 2 gm orally daily plus PA for 4 more weeks in an open label basis.

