resistance level: light, moderate, or hard. The resistance exercise sessions are to be completed 3 days a week, allowing at least 48 hours between each session. This allows the muscles adequate time for rest and prevents overtraining. The participant will begin with 1 set of 10 to 12 repetitions at lightest resistance progressing to 2 sets of 12 repetitions as exercise tolerance increases. Resistance will then be increased as the participant's endurance and strength progresses. The graded resistance program will be designed so that the individual begins with a lighter resistance and progresses to heavier resistance once a level has been mastered. Since the level of aerobic fitness will vary among participants, the frequency and duration of the walking program will be established based on exercise physiologist's assessment of the participant's baseline aerobic fitness level (six-minute walk test). For example, the recommendation may be to walk 10 minutes 1-3 times a day or up to a 30-minute walk once a day at a moderate intensity level. Participants will work toward the goal of 150 minutes of moderate intensity walking per week.

To encourage and monitor adherence to the walking program, we will provide participants with a pedometer and an exercise log to record their resistance exercise sessions, time spent in moderate intensity walking, and the number of steps they take each day. Participants will be asked to walk a minimum of 5 days a week at the duration established by the exercise physiologist. In the first week of the intervention, the exercise physiologist will meet with each participant to evaluate his or her current strength and aerobic fitness level and to teach the assigned exercises. Each week the exercise physiologist will assess their progress and help them identify and overcome any barriers to completing the exercise program, and to evaluate for adverse events or health problems. The frequency, intensity, and duration of the assigned exercises will also be evaluated and adjusted as necessary.

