The participants will be randomized to either the intervention described above or a control exercise program consisting of stretching exercises only. Participants in the control exercise intervention will meet with the exercise physiologist in the first week of the intervention in order to learn the stretches and receive written instructions on how they should be done. Participants will have weekly supervised sessions with an ACSM-certified cancer exercise specialist. With use of an outcome measures outlined in Table 1, we will analyze differences between participants receiving the exercise intervention and the control physical activity.

To ensure adherence to the exercise protocol, video recordings will be made. [name] will randomly review sessions to evaluate the exercise physiologist's adherence to the protocol.

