### **7.3. Safety**

All subjects who receive at least one dose of study treatment will be valid for the safety analysis. All observations pertinent to the safety of the study treatment will be recorded and included in the final report.

Safety variables include the following: AEs, laboratory changes (complete blood counts, electrolytes, chemistry, and coagulation), changes in vital signs (blood pressure, heart rate, respiratory rate, and temperature) and ECG and, in some instances, changes in chest x-ray images, as produced at the investigator's discretion (e.g., for evaluation for pneumonia).

All AEs whether considered drug-related or not, will be reported in with a diagnosis, start/stop dates, action taken, whether treatment was discontinued, any corrective measures taken, outcome, and other possible causes. For all events, the relationship to treatment and the intensity of the event will be determined by the investigator.

This trial will use the NCI-CTCAE v4.0 criteria for assessment of toxicity and SAE reporting with regard to toxicity grade.

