### **Interim Analysis Plan**

We plan to implement the Bayesian toxicity monitoring rule for severe toxicity (defined as any Grade 3 or 4 toxicity that is attributable to the FISH OIL treatment regimen as per NCI CTCAE V4 criteria) separately for each arm. We will stop the treatment arm if there is an 85% posterior probability to observe a larger than 30% severe toxicity rate in that arm, i.e.,  $Pr(P_{tox} > 0.3 | \text{data}) > 0.85$ , given that the prior of severe toxicity rate follows a beta distribution,  $\text{beta}(0.3, 0.7)$ . The cohort of monitoring will be every 5 patients starting from the first 10 patients. Given this rule, the accrual for a specific arm will be stopped if  $[\# \text{ severe toxicities}/\text{Total } \# \text{ of patients treated}] \geq 5/10, 7/15, 9/20, 11/25, 12/30, 13/32$ . Given these boundaries, we will have a 5%, 27% and 67% chance to stop an arm early if the true severe toxicity rate is 20%, 30% and 40% for that arm, respectively.

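### The stretching control arm always receives placebo, so the capsule blind holds only between the two physical activity arms; secondary comparisons that use the control arm are not double-blind

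*Combined protocol and SAP*

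**What the plan says.** Section 6 (Treatments) allocates patients to icosapent ethyl plus physical activity, "or placebo plus physical activity, or placebo plus control PA(1:1:1) for 8 weeks". The Synopsis and Section 6.1 give the same three arms.

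Under Exercise Prescription, the active programme is resistance training three days a week with walking towards 150 minutes a week. The alternative is "a control exercise program consisting of stretching exercises only". Both programmes have weekly supervised sessions.

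On blinding, Section 4.1 says that consenting eligible patients "will be admitted to the double-blind phase of the study described below". Section 6.1 matches the capsules: "The placebo will be identical to the drug, but will contain methylcellulose as the inert ingredient". The subsection on icosapent ethyl (and Type of control in the Synopsis) gives the purpose: "The rationale for placebo and control arm for PA is to control for placebo effect, attention to participant's expectation", together with the subjective side of assessment. Section 6.2 deals only with breaking the code for safety reporting and emergencies. It does not say who is masked, or to what.

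On safety, Section 7.3 says that "the relationship to treatment and the intensity of the event will be determined by the investigator", and the Interim Analysis Plan counts Grade 3 or 4 toxicity "attributable to the FISH OIL treatment regimen as per NCI CTCAE V4 criteria", arm by arm.

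The control arm is used in an exercise-versus-control analysis (Exercise Prescription), a three-group ANOVA or Kruskal-Wallis test of FACIT-F change (Section 8), repeated-measures analyses, and tables of toxicity by treatment, grade and relationship.

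**The concern.** Matching the capsules protects the blind only if nothing else reveals which capsule a patient takes. Here the exercise programme does. It is visible to the patient and the exercise staff, and one of its two values occurs with placebo only. The plan does not acknowledge this, and it gives no step to limit the consequences.

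Two kinds of secondary result are at stake.

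- **Efficacy on self-report.** A patient in placebo plus physical activity may reasonably hope to be on active drug. A stretching patient who knows the design cannot. Part of any fatigue difference between those arms could reflect expectation about the capsule and not the exercise. The six-minute walk, done with strong encouragement (Section 7.2.1), is open to the same influence.
- **Drug attribution in the control arm.** Causality is a yes/no judgement for each study treatment (Section 7.3.2.3). A rater who infers placebo may answer no for the drug almost automatically. A table of toxicity by relationship would then show too few drug-related events in that arm compared with the other two.

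**Working it through.** **1. The plan's own figures.** Inputs from Section 8: difference 9.5 − 3 = 6.5, SD 10, two-sided alpha 0.10, 30 per arm.

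- Noncentrality = 6.5 / (10 × √(2/30)) = 2.52 on 58 df, giving power 0.800 (0.809 by the normal approximation). The stated 80% reproduces.
- Single-group test in the control arm: 0.465 × √30 = 2.55 on 29 df, giving power 0.800. This also reproduces.
- Dropout: 30 / 0.95 = 31.6, rounded up to 32 per arm; 3 × 32 = 96.

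None of these depends on blinding in the control arm.

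**2. What the exercise programme reveals.** With 32 patients per arm:

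| What is known | Chance of active capsules |
|---|---|
| Three-arm design only | 32/96 = 1/3 |
| Design, and patient is on stretching | 0/32 = 0 |
| Design, and patient is on physical activity | 32/64 = 1/2 |

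The capsule can be deduced in one arm of three (32/96 = 33%). It stays evenly balanced in the two arms of the primary test.

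**3. Who can make the inference.** Exercise staff know the programme by definition. In the active programme they also meet patients weekly, among other things "and to evaluate for adverse events or health problems"; the text on the stretching arm gives weekly sessions without repeating that duty. For the investigator who rates causality, and for the research nurse who administers assessments (Section 4.1), the plan does not say whether the programme is known. For patients, it depends on what the consent document (referenced in Section 11.2, not in the text reviewed) says about the arms.

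**4. Effect on toxicity monitoring.** The rule stops an arm when Pr(p > 0.3 | data) > 0.85, with posterior beta(0.3 + x, 0.7 + n − x).

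- All the boundaries reproduce: 5/10 gives posterior probability 0.890, 12/30 gives 0.867, 13/32 gives 0.890.
- Exact stopping probabilities at true rates of 20%, 30% and 40% are 4.6%, 27.5% and 67.9% with the look at 32, or 4.6%, 26.9% and 66.5% without it. The plan states 5%, 27% and 67%.
- The posterior uses only x and n from the same arm. Attribution in the control arm therefore cannot move the icosapent boundary.
- At the extreme, a rater who attributes nothing to the drug in the control arm makes x = 0 throughout, and that arm's stopping probability is 0.

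**5. Comparisons affected.**

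| Comparison | Chance of active capsule, given programme | Capsule blind |
|---|---|---|
| Icosapent + PA vs placebo + PA (primary) | 1/2 vs 1/2 | Not broken by exercise |
| Exercise vs control PA | 1/2 vs 0 | Not protected |
| Three-group FACIT-F | 1/2, 1/2, 0 | Not protected for control arm |
| Drug-related toxicity, all three arms | 1/2, 1/2, 0 | Not protected for control arm |

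**The case against.** **Limited consequence.** The control arm is outside the primary test. It is sized for a single-group test, and Section 8 says it is not to be compared with the fish oil and exercise arm. The hypothesis about physical activity is worded as a change from baseline to week 8, and the study is described as small and exploratory. This stands, and it confines the point to secondary results. It does not remove it, because the three-group and exercise-versus-control comparisons are planned and do use this arm.

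**Exercise cannot be blinded anyway.** Stretching and resistance training look different under any design, so some expectation gap would remain even with a fourth arm. That is true. Knowledge of the capsule adds to that gap by an amount the documents do not let us measure.

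**Stronger readings that the documents do not support.**

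- A reader might infer that the blind is broken for every control patient from the first day. For patients this depends on consent wording that was not available and on recognising stretching as the control.
- A reader might infer that the control arm is useless for expectation. It still matches capsule-taking and weekly supervised contact, and the stated rationale covers the placebo as well, which does its job in the placebo plus physical activity arm.
- A reader might infer that the plan promises blinded toxicity attribution. It does not. It labels the phase double-blind and gives attribution to the investigator.
- A reader might size the bias from the 3.1-point placebo improvement in the dexamethasone trial and set it against the 6.5-point target. The 3.1 is a change from baseline at Day 15 in another trial and may include natural course and regression to the mean. The 6.5 belongs to the primary comparison, which is unaffected.

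**Conclusion.** The point holds for secondary comparisons. The design reveals placebo for 32 of 96 patients to anyone who knows both the arms and the exercise programme, so the double-blind description is correct only between icosapent plus physical activity and placebo plus physical activity. The control arm does not equalise capsule expectation in the way the stated rationale implies.

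The primary comparison, its 80% power and the icosapent arm's toxicity boundary stand, and no figure in the plan is wrong on this account. The bias in the exercise-versus-control result, the three-group result and control-arm attribution is of unknown size. It rests on two things the documents do not settle: what patients are told about the arms, and which assessors learn the programme.

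**What to change.** 1. In Sections 4.1 and 6.2, state that the capsule blind applies only between the two physical activity arms. Report the three-group and exercise-versus-control results as not blinded for the control arm.
2. Base any drug-versus-placebo comparison of attributable toxicity on the two physical activity arms. Alongside it, show adverse events of any cause for all three arms. Section 7.3 already records events whether or not they are thought drug-related, so no new data are needed.
3. Describe both exercise programmes neutrally to participants. Have existing staff give the questionnaires and the six-minute-walk encouragement from a fixed script, unaware of the programme where feasible.

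I would not ask for the investigator who assigns causality to be masked to the programme. Section 7.3.2.3 requires a separate judgement for each study treatment, the paragraph after it adds protocol-required procedures, and Section 11.1 has the Principal Investigator personally overseeing treatment.

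Nor is a fourth arm (icosapent plus stretching) needed. At 32 per arm it would raise the total to 4 × 32 = 128. Keeping 96 would leave 24 per arm, about 22 to 23 evaluable after 5% dropout, and cut power for the present primary comparison to about 68–70%.

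The cost is a less favourable description of the control-arm comparisons and minor changes to staff routing. No patients or staff are added, and no sample size changes.

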### **6.1 Treatments to be administered**

In this study, patients will be randomized to either combination of Icosapent ethyl 2 gm orally daily plus physical activity; or placebo plus PA or placebo plus control PA for 8 weeks (See Fig. 3 below for the treatment schema). The placebo will be identical to the drug, but will contain methylcellulose as the inert ingredient. Assessment will be performed at baseline to Day  $57\pm5$  as per Table 4.

#### **Icosapent ethyl (Vascepa)**

In the proposed study we plan to use fish oil preparation, Icosapent *ethyl* [an ethyl ester of EPA] 0.5 gram capsules [Amarin Pharma Inc, Bedminster, NJ, 2012]. The placebo will be identical to the drug, but will contain methylcellulose as the inert ingredient. Assessment will be performed at baseline to Day  $57\pm5$ . The objective of 8 weeks of treatment is to evaluate the efficacy of the combined intervention for cancer related fatigue.

The rationale for placebo and control arm for PA is to control for placebo effect, attention to participant's expectation and the subjective elements of diagnosis or assessment. See Table 4 for the study assessments. All patients at the primary end point (8 weeks) will have an option to receive Icosapent ethyl 2 gm orally daily plus PA for 4 more weeks in an open label basis.

#### Treatment Schema

### Figure 3

#### Exercise Prescription.

For this study, we plan to use an exercise intervention based on the American College of Sports Medicine (ACSM) exercise recommendations for cancer survivors. The exercise intervention will include resistance training 3 days/week and moderate intensity walking for up to 150 minutes per week.

Participants will have weekly supervised (in person or by telephone) sessions with an ACSM-certified cancer exercise specialist. At the supervised, in person session the patient will perform the resistance exercise and moderate intensity walking up to 30 minutes, depending on the patient's tolerance.

The goal of the resistance exercises is to enhance the individual's ability to go from a seated to standing position independently. The resistance exercise program has been designed to strengthen the major muscles of the lower body, including the quadriceps, hamstrings, gluteus maximus, and hip flexor group.

These exercises will include (but will not be limited to) squats, lunges, leg extensions, leg curls, and hip extensions. We focus on the lower body to simplify the exercise plan, given the short timeframe of the intervention, and because lower body strength is critical to patient mobility and functioning. We will use resistance tubes as our mode of resistance. These tubes are color-coded to indicate their specific

resistance level: light, moderate, or hard. The resistance exercise sessions are to be completed 3 days a week, allowing at least 48 hours between each session. This allows the muscles adequate time for rest and prevents overtraining. The participant will begin with 1 set of 10 to 12 repetitions at lightest resistance progressing to 2 sets of 12 repetitions as exercise tolerance increases. Resistance will then be increased as the participant's endurance and strength progresses. The graded resistance program will be designed so that the individual begins with a lighter resistance and progresses to heavier resistance once a level has been mastered. Since the level of aerobic fitness will vary among participants, the frequency and duration of the walking program will be established based on exercise physiologist's assessment of the participant's baseline aerobic fitness level (six-minute walk test). For example, the recommendation may be to walk 10 minutes 1-3 times a day or up to a 30-minute walk once a day at a moderate intensity level. Participants will work toward the goal of 150 minutes of moderate intensity walking per week.

To encourage and monitor adherence to the walking program, we will provide participants with a pedometer and an exercise log to record their resistance exercise sessions, time spent in moderate intensity walking, and the number of steps they take each day. Participants will be asked to walk a minimum of 5 days a week at the duration established by the exercise physiologist. In the first week of the intervention, the exercise physiologist will meet with each participant to evaluate his or her current strength and aerobic fitness level and to teach the assigned exercises. Each week the exercise physiologist will assess their progress and help them identify and overcome any barriers to completing the exercise program, and to evaluate for adverse events or health problems. The frequency, intensity, and duration of the assigned exercises will also be evaluated and adjusted as necessary.

The participants will be randomized to either the intervention described above or a control exercise program consisting of stretching exercises only. Participants in the control exercise intervention will meet with the exercise physiologist in the first week of the intervention in order to learn the stretches and receive written instructions on how they should be done. Participants will have weekly supervised sessions with an ACSM-certified cancer exercise specialist. With use of an outcome measures outlined in Table 1, we will analyze differences between participants receiving the exercise intervention and the control physical activity.

To ensure adherence to the exercise protocol, video recordings will be made. [name] will randomly review sessions to evaluate the exercise physiologist's adherence to the protocol.

## **6.2 Blinding**

In compliance with applicable regulations, in the event of a SUSARs, the patient's treatment code will usually be unblinded before reporting to the health authorities, ethic committees and investigators (see Section 7.3.3.3) if the SUSAR was related to the blinded treatment.

### **Emergency unblinding by the investigator**

Unblinding may occur for emergency purposes only. Investigators should note that the occurrence of a serious adverse event or progressive disease should not routinely precipitate the immediate unblinding of the label. If unblinding is necessary for the treatment of a subject for a serious adverse event, every

attempt should be made to contact the Principal Investigator prior to unblinding. If this is not feasible, then Principal Investigator must be contacted within 24 hours of unblinding.

